10.4 Post-Treatment Follow-Up

Assessments for subjects who have completed durvalumab and tremelimumab treatment and achieved disease control, or have discontinued durvalumab or tremelimumab due to toxicity in the absence of confirmed progressive disease are provided in Appendix 2.

Assessments for subjects who have discontinued durvalumab or tremelimumab treatment due to confirmed PD are presented in Appendix 3.

11.1 TOXICITIES/SIDE EFFECTS

The common terminology criteria for adverse events version 4.0 (CTCAE v4.0) will be used to grade the severity of adverse events.

11.1 Schedule modification and toxicity management

For adverse events (AEs) that are considered at least possibly due to administration of durvalumab or tremelimumab the following adjustment guidance may be applied:

- Treat each of the toxicities with maximum supportive care (including holding the agent suspected of causing the toxicity where required).
- If the symptoms promptly resolve with supportive care, consideration should be given to continuing durvalumab or tremelimumab along with appropriate continuing supportive care. If medically appropriate, modifications to the schedule are permitted for durvalumab and tremelimumab (see Appendix 1).
- All schedule modifications should be documented with clear reasoning and documentation of the approach taken.
- Dose reductions are not permitted.

In addition, there are certain circumstances in which durvalumab or tremelimumab should be permanently discontinued.

Following the first dose of durvalumab or tremelimumab, subsequent administration of durvalumab or tremelimumab can be modified based on toxicities observed (see Appendix 1). Dose reductions are not permitted.

Based on the mechanism of action of durvalumab or tremelimumab leading to T-cell activation and proliferation, there is the possibility of observing immune related Adverse Events (irAEs) during the conduct of this study. Potential irAEs include immune-mediated enterocolitis, dermatitis, hepatitis, and endocrinopathies. Subjects should be monitored for signs and symptoms of irAEs. In the absence of an alternate etiology (e.g., infection or PD) signs or symptoms of enterocolitis, dermatitis, hepatitis, and endocrinopathy should be considered to be immune-related.

Schedule modification recommendations and toxicity management guidelines for immune-mediated reactions, for infusion-related reactions, and for non-immune-mediated reactions are detailed in Appendix 1. As outlined in Appendix 1, patients may temporarily suspend study treatment for up to 12 weeks beyond the scheduled date of delayed infusion if study drug-related toxicity requiring dose suspension is experienced. If study drug is held because of AEs for > 12 weeks beyond the scheduled date of infusion, the patient will be discontinued from study therapy. Inability to reduce corticosteroid to a dose of ≤ 10 mg of prednisone per day (or equivalent) within 12 weeks after last dose of study drug/regimen will result in study discontinuation. Recurrence of a previously experienced Grade 3 treatment-related AE following resumption of dosing will result in study discontinuation. Patients who discontinue study therapy due to toxicity will be followed as outlined in Appendix 2 or 3. Dose interruptions for reasons other than toxicity, such as surgical procedures, may be allowed. The acceptable length of interruption will be at the discretion of the Sponsor.

11.2 Definition of adverse events

The International Conference on Harmonization (ICH) Guideline for Good Clinical Practice (GCP) E6 (R1) defines an AE as:

Any untoward medical occurrence in a patient or clinical investigation subject administered a pharmaceutical product and which does not necessarily have a causal relationship with this treatment. An AE can therefore be any unfavorable and unintended sign (including an abnormal laboratory finding), symptom, or disease temporally associated with the use of a medicinal product, whether or not considered related to the medicinal product.

An AE includes but is not limited to any clinically significant worsening of a subject's pre-existing condition. An abnormal laboratory finding (including ECG finding) that requires an action or intervention by the investigator, or a finding judged by the investigator to represent a change beyond the range of normal physiologic fluctuation, should be reported as an AE.

Adverse events may be treatment emergent (i.e., occurring after initial receipt of investigational product) or nontreatment emergent. A nontreatment-emergent AE is any new sign or symptom, disease, or other untoward medical event that begins after written informed consent has been obtained but before the subject has received investigational product.

Elective treatment or surgery or preplanned treatment or surgery (that was scheduled prior to the subject being enrolled into the study) for a documented pre-existing condition, that did not worsen from baseline, is not considered an AE (serious or nonserious). An untoward medical event occurring during the prescheduled elective procedure or routinely scheduled treatment should be recorded as an AE or SAE. The term AE is used to include both serious and non-serious AEs.

The description and reporting of serious adverse events (SAEs) are outlined in section 17.2.

11.3 Durvalumab + tremelimumab adverse events of special interest

An adverse event of special interest (AESI) is one of scientific and medical interest specific to understanding of the Investigational Product and may require close monitoring and rapid communication by the investigator to the sponsor. An AESI may be serious or non-serious. The rapid reporting of AESIs allows ongoing surveillance of these events in order to characterize and understand them in association with the use of this investigational product.

AESIs for durvalumab ±tremelimumab include but are not limited to events with a potential inflammatory or immune-mediated mechanism and which may require more frequent monitoring and/or interventions such as steroids, immunosuppressants and/or hormone replacement therapy. These AESIs are being closely monitored in clinical studies with durvalumab monotherapy and combination therapy. An immune-mediated adverse event (imAE) is defined as an AESI that is associated with drug exposure and is consistent with an immune-mediated mechanism of action and where there is no clear alternate etiology. Serologic, immunologic, and histologic (biopsy) data, as appropriate, should be used to

support an imAE diagnosis. Appropriate efforts should be made to rule out neoplastic, infectious, metabolic, toxin, or other etiologic causes of the imAE.

If the Investigator has any questions in regards to an event being an imAE, the Investigator should promptly contact the Principal Investigator or Co-Principal Investigator.

AESIs observed with durvalumab ± tremelimumab include:

- Diarrhea / Colitis and intestinal perforation
- Pneumonitis / ILD
- Hepatitis / Transaminase increases
- Endocrinopathies (i.e. events of hypophysitis/hypopituitarism, adrenal insufficiency, hyper- and hypothyroidism and type I diabetes mellitus)
- Rash / Dermatitis
- Nephritis / Blood creatinine increases
- Pancreatitis / serum lipase and amylase increases
- Myocarditis
- Myositis / Polymyositis
- Neuropathy / neuromuscular toxicity (e.g. Guillain-Barré, and myasthenia gravis)
- Other inflammatory responses that are rare / less frequent with a potential immune-mediated aetiology include, but are not limited to, pericarditis, sarcoidosis, uveitis and other events involving the eye, skin, haematological and rheumatological events.

In addition, infusion-related reactions and hypersensitivity/anaphylactic reactions with a different underlying pharmacological aetiology are also considered AESIs.

Further information on these risks (e.g. presenting symptoms) can be found in the current version of the durvalumab and tremelimumab Investigator's Brochures. More specific guidelines for their evaluation and treatment are described in detail in the Dosing Modification and Toxicity Management Guidelines (please see Appendix 1). These guidelines have been prepared by the Sponsor to assist the Investigator in the exercise of his/her clinical judgment in treating these types of toxicities. These guidelines apply to AEs considered causally related to the study drug/study regimen by the reporting investigator.

If new or worsening pulmonary symptoms (e.g. dyspnea) or radiological abnormality suggestive of pneumonitis/interstitial lung disease is observed, toxicity management as described in detail in the Dosing Modification and Toxicity Management Guidelines (see Appendix 1) will be applied. The results of the full diagnostic workup (including high-

resolution computed tomography (HRCT), blood and sputum culture, hematological parameters etc) will be captured in the eCRF. It is strongly recommended to perform a full diagnostic workup, to exclude alternative causes such as lymphangitic carcinomatosis, infection, allergy, cardiogenic edema, or pulmonary hemorrhage. In the presence of confirmatory HRCT scans where other causes of respiratory symptoms have been excluded, a diagnosis of pneumonitis (ILD) should be considered and the Dosing Modification and Toxicity Management Guidelines should be followed.

Pneumonitis (ILD) investigation

The following assessments, and additional assessments if required, will be performed to enhance the investigation and diagnosis of potential cases of pneumonitis. The results of the assessment will be collected.

- Physical examination
 - Signs and symptoms (cough, shortness of breath and pyrexia, etc.) including auscultation for lung field will be assessed.
- SpO2
 - Saturation of peripheral oxygen (SpO2)
- Other items
 - When pneumonitis (ILD) is suspected during study treatment, the following markers should be measured where possible and deemed appropriate by the treating physician:
 - (i) ILD Markers (KL-6, SP-D) and β-D-glucan
 - (ii) Additional Clinical chemistry: CRP, LDH

11.4 Immune-related adverse events

Based on the mechanism of action of durvalumab and tremelimumab leading to T-cell activation and proliferation, there is a possibility of observing irAEs during the conduct of this study. Potential irAEs may be similar to those seen with the use of ipilimumab, BMS-936558 (anti-PD-1 mAb), and BMS-936559 (anti-PD-L1 mAb) and may include immune-mediated enterocolitis, dermatitis, hepatitis (hepatotoxicity), pneumonitis, and endocrinopathies (49–51). These AEs are inflammatory in nature and can affect any organ. With anti-PD-L1 and anti-CTLA-4 combination therapy, the occurrence of overlapping or increasing cumulative toxicities that include irAEs could potentially occur at higher frequencies than with either durvalumab or tremelimumab monotherapy. Patients should be monitored for signs and symptoms of irAEs. In the absence of an alternate etiology (e.g., infection or PD), an immune-related etiology should be considered for signs or symptoms of enterocolitis, dermatitis, pneumonitis, hepatitis, and endocrinopathy. In addition to the dose modification

guidelines provided in Appendix 1, it is recommended that irAEs are managed according to the general treatment guidelines outlined for ipilimumab (52). These guidelines recommend the following:

- Patients should be evaluated to identify any alternative etiology.
- In the absence of a clear alternative etiology, all events of an inflammatory nature should be considered immune related.
- Symptomatic and topical therapy should be considered for low-grade events.
- Systemic corticosteroids should be considered for a persistent low-grade event or for a severe event.
- More potent immunosuppressives should be considered for events not responding to systemic steroids (e.g., infliximab or mycophenolate).
- If the Investigator has any questions in regards to an AE being an irAE, the Investigator should immediately contact the Study Physician.

11.5 Criteria for Hy's Law (FDA Guidance 2009)

- The drug causes hepatocellular injury, generally shown by a higher incidence of 3-fold or greater elevations above the ULN of ALT or AST than the (non-hepatotoxic) control drug or placebo
- Among trial subjects showing such aminotransferase elevations, often with aminotransferases much greater than 3 x ULN, one or more also show elevation of serum total bilirubin to >2 x ULN, without initial findings of cholestasis (elevated serum alkaline phosphatase)
- No other reason can be found to explain the combination of increased aminotransferases and total bilirubin, such as viral hepatitis A, B, or C; pre-existing or acute liver disease; or another drug capable of causing the observed injury.

12.1 CRITERIA FOR THERAPEUTIC RESPONSE/OUTCOME ASSESSMENT

Patients will be assessed every cycle by physical examination for response for disease progression. Patients will have appropriate radiographic diagnostic procedures (CT scan of chest and CT or MRI of abdomen and pelvis) for evaluation of measurable disease at baseline within 28 days of initiation of the study. Imaging will be repeated to evaluate the disease every 2 cycles while patients are on study.

12.2 Response Criteria

The response evaluation criteria in solid tumors (RECIST 1.1) will be used as presented in Appendix 4. The immune-related RECIST (irRECIST) criteria will also be used as a response

assessment as described in Appendix 5.

12.3 Confirmation

The main goal of confirmation of objective response is to avoid overestimating the response rate observed. In cases where confirmation of response is not feasible, it should be made clear when reporting the outcome of such studies that the responses are not confirmed.

To be assigned a status of PR or CR, changes in tumor measurements must be confirmed by repeat assessments that should be performed no less than 4 weeks after the criteria for response are first met. Longer intervals as determined by the study protocol may also be appropriate.

In the case of SD, follow-up measurements must have met the SD criteria at least once after study entry at a minimum interval (in general, not less than 6-8 weeks) that is defined in the study protocol.

13.1 CRITERIA FOR REMOVAL FROM STUDY

An individual subject will not receive any further investigational product if any of the following occur in the subject in question:

- Withdrawal of consent or lost to follow-up. If consent is withdrawn, the subject will not receive any further investigational product or further study observation. Note that patients may withdraw from treatment without withdrawing consent for the study. Such patients will receive no further investigational treatment but can be followed for progression and survival. Documentation distinguishing these two outcomes should be placed in the patient's chart.
- Adverse event that, in the opinion of the investigator or the sponsor, contraindicates further dosing
- Subject is determined to have met one or more of the exclusion criteria for study participation at study entry and continuing investigational therapy might constitute a safety risk
- Pregnancy or intent to become pregnant
- Any AE that meets criteria for discontinuation as defined in Section 11.0
- Grade ≥ 3 infusion reaction
- Subject noncompliance that, in the opinion of the investigator, warrants withdrawal; e.g., refusal to adhere to scheduled visits
- Initiation of alternative anticancer therapy including another investigational agent

- Prolonged duration of therapy-related toxicity as defined in section 11.2.
- Patients may be permitted to continue study treatment after RECIST v1.1-defined progressive disease if they meet all of the following criteria:
 - Absence of symptoms and signs (including worsening of laboratory values [e.g. new or worsening hypercalcemia]) indicating unequivocal progression of disease
 - No decline in ECOG performance status from baseline
 - Absence of tumor growth at critical anatomic sites (e.g. leptomeningeal disease) that cannot be managed by protocol-allowed medical interventions
 - Evidence of clinical benefit (defined as the stabilization or improvement of disease-related symptoms) as assessed by the investigator.

Patients for whom radiographic disease progression is confirmed at subsequent tumor assessments may be considered for continued study treatment at the discretion of the investigator if they continue to meet the criteria above and have evidence of clinical benefit.

Subjects who are permanently discontinued from further receipt of investigational product, regardless of the reason (withdrawal of consent, due to an AE, other), will be identified as having permanently discontinued treatment.

Subjects who are permanently discontinued from receiving investigational product will be followed per section 9.4 for safety, including the collection of any protocol-specified blood specimens, unless consent is withdrawn or the subject is lost to follow-up or enrolled in another clinical study. All subjects will be followed for survival. Subjects who decline to return to the site for evaluations will be offered follow-up by phone every 3 months as an alternative.

14.1 BIOSTATISTICS

14.2 Primary Endpoint and Sample Size Justification

The three histologic groups (Small-Cell, Squamous Cell Carcinoma, and Adenocarcinoma) will be part of the same cohort given they are expected to have similar response rates. With an unacceptable rate of 5% and acceptable rate of 20%, and setting type I error to 5% and power to 80%, with Simon's minimax two-stage design, we will enroll 13 patients in the first stage. Non-transitional cell carcinoma of the urothelial tract is a rare entity. Single, arm phase II studies have been published, but only in the front-line setting and only in small cohorts of patients (summarized in table 1). To our knowledge, there is no published data on response rates to second-line chemotherapy in patients with non-transitional cell carcinoma of the urothelial tract. The patient population under study has no standard treatment options and, in our group's clinical experience, rarely experiences a meaningful clinical benefit from chemotherapy. Therefore, we have elected to set the null hypothesis at an ORR of 5%. If no

patients in the first 13 have achieved a response, enrollment for stage 2 will be halted until the 13 subjects in the first stage have been assessed for response (window of 2 disease assessment scans following initiation of treatment). If we see 1 or more responses in any of the histologies in the first stage, we continue to the second stage where we will enroll additional 14 patients. If, at the end of the study, we see 4 or more responses out of the total of 27 patients, we will consider the therapy promising. As an exploratory analysis, we will also estimate the response rate of the small cell/neuroendocrine, predominant squamous, and predominant adenocarcinoma cohorts separately as a proportion of responders with the corresponding confidence interval, although formal comparisons between the three cohorts are not planned.

The response evaluable population is defined as all patients with a baseline disease assessment who have received at least one treatment with durvalumab and tremelimumab on study and have had either at least one post-baseline disease assessment or withdrawn from study treatment prior to post-baseline disease assessment due to clinical progression or death.

As described in section 9.2, patients may undergo retreatment after disease progression. The primary endpoint of best overall response is based on the best response from the first round of treatment.

Patients who discontinue protocol therapy for toxicity will be followed for response per Appendix 2. Patient who come off study for withdrawal of consent prior to having one post-baseline disease assessment will be considered inevaluable and will be replaced. All treated patients will remain evaluable for toxicity.

With an estimated patient accrual of 1 patient every month, it would take approximately 13-30 months to complete accrual to the trial.

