1.0 PROTOCOL SUMMARY AND/OR SCHEMA

This is a phase II study testing durvalumab and tremelimumab in metastatic, non-transitional cell carcinoma of the urothelial tract. Patients with I) any component of small cell carcinoma (or neuroendocrine features) II) predominant squamous cell carcinoma or III) predominant adenocarcinoma of the urothelial tract will be enrolled. A Simon's minimax two-stage design will be carried out. We will enroll 13 patients in the first stage. If we see 1 or more responses in the first stage, we continue to the second stage where we enroll an additional 14 patients for a total sample size of 27 patients. Patients will be treated in 4-week cycles. Patients will receive 4 cycles of the combination of durvalumab and tremelimumab followed by up to 9 cycles of durvalumab maintenance or until lack of clinical benefit or unacceptable toxicity. Cross-sectional imaging will be performed every 8 weeks until the end of treatment. The best, confirmed overall response rate (ORR) by RECIST 1.1 will be determined as the primary endpoint.

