4.1 OVERVIEW OF STUDY DESIGN/INTERVENTION

4.2 Design

This is a single-arm, phase II study with a Simon minimax design testing the combination of durvalumab and tremelimumab in patients with non-TCC of the urothelial tract. In the first stage, 13 patients will be accrued. If there are no responses in these 13 patients, the study will be stopped. Otherwise, 14 additional patients will be accrued for a total of 27. The null hypothesis will be rejected if 4 or more responses are observed in 27 patients. See section 14 for more details regarding statistical design.

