10.3 Radiographic Studies During Treatment

Patients will undergo cross-sectional imaging every 2 cycles (\pm 7 days) until lack of clinical benefit. CT chest may be with or without contrast. MRI chest may be performed if patients refuse CT. Abdomen/Pelvis imaging should include IV contrast unless there is an extenuating circumstance approved by the PI. CT scans of the abdomen/pelvis and MRI abdomen/pelvis are both acceptable. Imaging will be evaluated using RECIST v1.1.

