^a “Non-CR/non-PD” is preferred over “stable disease” for non-target disease since stable disease is increasingly used as an endpoint for assessment of efficacy in some trials; thus, assigning “stable disease” when no lesions can be measured is not advised.

B. Missing Assessments and Not-Evaluable Designation

When no imaging/measurement is done at all at a particular timepoint, the patient is not evaluable at that timepoint. If only a subset of lesion measurements are made at an assessment, usually the case is also considered not evaluable at that timepoint, unless a convincing argument can be made that the contribution of the individual missing lesion(s) would not change the assigned timepoint response. This would be most likely to happen in the case of PD. For example, if a patient had a baseline sum of 50 mm with three measured lesions and, during the study, only two lesions were assessed, but those gave a sum of 80 mm; the patient will have achieved PD status, regardless of the contribution of the missing lesion.

If one or more target lesions were not assessed either because the scan was not done or the scan could not be assessed because of poor image quality or obstructed view, the response for target lesions should be “unable to assess” since the patient is not evaluable. Similarly, if one or more non-target lesions are not assessed, the response for non-target lesions should be “unable to assess” except where there is clear progression. Overall response would be “unable to assess” if either the target response or the non-target response is “unable to assess,” except where this is clear evidence of progression as this equates with the case being not evaluable at that timepoint.

Table 3. Best Overall Response When Confirmation Is Required

Overall Response at First Timepoint	Overall Response at Subsequent Timepoint	Best Overall Response
CR	CR	CR
CR	PR	SD, PD, or PR ^a
CR	SD	SD, provided minimum duration for SD was met; otherwise, PD
CR	PD	SD, provided minimum duration for SD was met; otherwise, PD
CR	NE	SD, provided minimum duration for SD was met; otherwise, NE
PR	CR	PR
PR	PR	PR
PR	SD	SD
PR	PD	SD, provided minimum duration for SD was met; otherwise, PD
PR	NE	SD, provided minimum duration for SD was met; otherwise, NE
NE	NE	NE

CR = complete response; NE = not evaluable; PD = progressive disease; PR = partial response;
 SD = stable disease.

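### Could the stage-1 rule stop the trial while a response first seen at the second scan is still awaiting confirmation?

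*Combined protocol and SAP*

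**What the plan says.** - **Stage-1 rule.** Section 4.2: "If there are no responses in these 13 patients, the study will be stopped". Section 14.2 opens stage 2 on one or more responses. If none has been seen in the first 13, it pauses stage-2 enrollment until those 13 are assessed, over a "window of 2 disease assessment scans following initiation of treatment". Neither section attaches the word confirmed or unconfirmed to these responses.
- **Endpoint.** Section 1.0: "The best, confirmed overall response rate (ORR) by RECIST 1.1 will be determined as the primary endpoint".
- **Confirmation.** Section 12.3 requires that "changes in tumor measurements must be confirmed by repeat assessments that should be performed no less than 4 weeks after the criteria" were initially satisfied.
- **Scan schedule.** Section 10.3: "Patients will undergo cross-sectional imaging every 2 cycles". A cycle is 4 weeks, so scans fall at about weeks 8, 16 and 24.
- **Accrual.** Section 14.2 plans "With an estimated patient accrual of 1 patient every month".
- **Design.** Section 14.2 sets a 5% unacceptable rate, a 20% acceptable rate, 5% type I error and 80% power, with 13 then 14 patients. The therapy is called promising at 4 or more responses in 27.

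**The concern.** The window closes at about week 16. A response first seen at scan 1 can be confirmed at scan 2. One first seen at scan 2 can be confirmed at week 20 at the earliest, or at week 24 on the scheduled scan. If the stage-1 rule inherits the endpoint's confirmation requirement, a patient with a fresh PR at scan 2 is not yet a responder when the window ends.

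The rule turns on 0 versus 1 response in 13, so a single such patient could decide whether the trial continues. Two teams could take opposite decisions from the same data, and one of them would close a rare-disease trial with its only response still pending. Appendix 4, Table 3 seems to make this worse: it scores a PR followed by a non-evaluable timepoint as "SD, provided minimum duration for SD was met; otherwise, NE".

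**Working it through.** **1. Reproduce the stated design** (exact binomial; stop at 0/13, promising at 4 or more of 27; inputs from section 14.2).

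Early stop = (1 − p)^13. At p = 0.20 this is 0.8^13 = 0.0550; at p = 0.05 it is 0.95^13 = 0.5133.

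Power = Σ over x ≥ 1 of P(x of 13) × P(at least 4 − x of 14), at p = 0.20:

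| x in stage 1 | P(x) | P(enough in stage 2) | product |
|---|---|---|---|
| 1 | 0.1787 | 0.5519 | 0.0986 |
| 2 | 0.2680 | 0.8021 | 0.2150 |
| 3 | 0.2457 | 0.9560 | 0.2349 |
| 4 or more | 0.2527 | 1 | 0.2527 |

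The total is 0.801 (0.8011 unrounded). The same sum at p = 0.05 gives a type I error of 0.0416. Expected N under the null is 13 + 14 × (1 − 0.5133) = 19.8. The design is correct as stated.

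**2. A pending response counts.** If the final count is still of confirmed responses and no response begins after scan 2, power remains 80.1%. Even if the futility stop never operated, type I error could not exceed P(4 or more of 27 at 5%) = 0.0437.

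**3. Only confirmed responses count, using every scan in hand.** At 1 patient per month, when patient 13 reaches week 16, patient 12 is at about week 20 and patient 11 at about week 24-25. So k = 1 patient lacks a confirming scan if confirmation is done at 4 weeks, and k = 2 if it waits for the scheduled third scan. Let f be the share of eventual confirmed responders already confirmed by scan 2. It is an assumption, taken as 0.5 to 0.9. The other 13 − k patients are taken as fully observed.

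False stop at 20% = 0.8^(13−k) × (1 − 0.2f)^k.

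- k = 1, f = 0.9: 0.0687 × 0.82 = 0.0563
- k = 2, f = 0.5: 0.0859 × 0.90² = 0.0696

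Power lost = P(no responder among the first 13 − k) × P(the pending patients include responders, none yet confirmed, and the total would reach 4).

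- k = 1, f = 0.9: 0.0687 × 0.2 × 0.1 × 0.5519 = 0.0008, leaving 80.0%
- k = 2, f = 0.5: 0.0859 × (0.32 × 0.5 × 0.5519 + 0.04 × 0.25 × 0.8021) = 0.0859 × 0.0963 = 0.0083, leaving 79.3%

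Type I error falls slightly in each case, because extra stopping can only reduce rejections.

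**4. The unfavorable extreme.** Suppose only confirmed responses count and each patient's scans after the second are discarded, so k = 13. False stop is then (1 − 0.2f)^13: 0.076, 0.104, 0.141 and 0.190 for f = 0.9, 0.8, 0.7 and 0.6. Power is 78.9%, 77.1%, 74.4% and 70.8%. This requires ignoring data already held: at the planned accrual patient 1 is over a year past first dose by then. No section asks for it.

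**5. What the text instructs.** In section 14.2 the two-scan window marks how long enrollment pauses; it does not say that the trial closes when the window does. The stop in section 4.2 applies when there are no responses, and a PR with its confirmatory scan due is not plainly that. Table 3 of Appendix 4 assigns best overall response when a timepoint was not evaluable. A scan that is not yet due is not such a timepoint, so the table does not classify a pending response.

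**The case for a change.** The strongest case for a change is that the rule is undefined exactly where it is most sensitive. Section 12.3 withholds PR or CR status until confirmation, so a confirmed-only reading is open. Section 14.3 itself acknowledges delayed responses with checkpoint blockade, so a first response at scan 2 is foreseeable. A choice made once the data are visible weakens a pre-specified rule, and a mistaken stop is hard to repair at 1 patient per month.

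Writing the rule down would also cost little. Suppose pending responses opened stage 2 and an assumed 2.5-5% of patients had a CR or PR that is never confirmed. Early stopping under the null would fall from 51% to between 0.95^12 × 0.925 = 50.0% and 0.95^11 × 0.90² = 46.1%. Expected N would rise from 19.8 to between 13 + 14 × 0.5002 = 20.0 and 13 + 14 × 0.5393 = 20.55.

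What stands is that the definition is unwritten and a clarifying sentence would do no harm. What does not stand is that the plan directs a stop with a response pending. The documents use confirmed where they want it, for the endpoint in section 1.0 and for duration of response in section 14.3, and leave it out of the stage-1 rule. Section 12.3 itself speaks of response criteria being met before they are confirmed. A team with one pending PR can wait for the next scan or open stage 2; either is a sensible use of the rule, and neither raises type I error above 5%.

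**Conclusion.** No change to the plan is needed. This is missing detail that analysts would fill sensibly. The natural reading loses nothing: power 80.1%, false stop 5.5%. The stricter reading, with all available scans used, costs at most about 0.8 percentage points of power (79.3-80.0%) and 1.5 points of false stop (5.6-7.0%). Type I error is at most 4.37% in every case, and the final rule and maximum sample size are unaffected.

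The size rests on two assumptions. The first is accrual close to 1 patient per month: with three patients pending and f = 0.5, power would be 78.8%. The second is f between 0.5 and 0.9, which the documents do not inform. The larger losses appear only if follow-up already collected is thrown away.
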